10.3 Participant compensation

Participants will receive a £15 high street voucher at six-week, 12-week, 20-week and 52-week outcome return, £60 in total.

10.4 Withdrawal from the study

Participants may withdraw from the study at any stage without providing any explanation and this will be communicated to them on the participant information sheet and verbally by both the research team and their therapist. If they withdraw before informed consent all data (including personal data) will be deleted. If withdrawal takes place after informed consent participants may request withdrawal of their data up until the point at which the study database is locked for analysis. This will be made clear in the participant information sheet and the informed consent form.

10.5 Randomisation and stratification

King's College London Clinical Trials Unit (KCTU) will provide a computer randomisation service. Stratification will be undertaken on diagnosis of PTSD or CPTSD, age and sex. Randomisation will take place after the eligibility confirmation assessment and once baseline data has been completed. Participants will be randomised to the intervention arm where they will receive therapy immediately or to the waiting list control.

Only three members of the research team will be unmasked: the lead clinical provider, the safety monitoring researcher and the trial statistician (the senior statistician will remain masked). All those entering data will be masked to treatment group. For participants randomised to the intervention group, therapy will commence within three weeks. If participant holidays are arranged, randomisation will be delayed ensuring this timeline can be maintained.

10.6 Proposed sample size

To detect a mean between group difference of 10-point drop in PCL-5 score (MCID) [54, 57] at 20 weeks, with a standard deviation of 20, taken from our feasibility trial [25] and 90% power (5% significant level), 172 in total (86 patients per group) are required. To allow for a loss to follow up of 20% at 20 weeks. The proposed 20% loss to follow up rate is informed by a review comparing TF-CBT with EMDR, research and treatment attrition ranged from 8–58% with a mean of 29% [17]. However, our feasibility loss to follow up was 20% so we will recruit 215 participants, over 19 months (12 patients per month). We will monitor recruitment to these goals in the internal pilot.

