1.6 Study Synopsis

Title Of Clinical Trial:	Efficacy and mechanisms evaluation of remotely delivered Fast Imagery Reversal Script for Trauma release Protocol (FIRST Protocol) vs Waiting List (WL) Controlled group for Post-Traumatic Stress Disorder (PTSD) in UK military veterans			
Protocol Short Title/ Acronym:	FIRST PETT			
Study Phase if not mentioned in title:	Phase 3			
Sponsor Name:	King's College London			
Chief Investigator:	[name]			
UKCRN Number:	ТВС			
REC Number:	ТВС			
Medical Condition Or Disease Under Investigation:	Post-Traumatic Stress Disorder			
Purpose Of Clinical Trial:	Evaluate the efficacy and mechanisms of remotely delivered Fast Imagery Reversal Script for Trauma Release Protocol (FIRST Protocol) vs Waiting List (WL) Controlled group for PTSD in UK military veterans			
Primary Objective:	Determine the efficacy of FIRST compared to wait list control at 20 weeks for achieving a Minimal Clinically Important Difference in PTSD symptoms.			
Secondary Objective(s):	 -Establish proof of concept of the remotely delivered FIRST protocol. - Understand the impacts of FIRST on mental health and wellbeing. -Understand 52-week FIRST maintenance of effect. -Determine whether the mechanistic pathways can be understood through established cognitive science of PTSD. 			
Trial Design:	Parallel group single masked (outcome assessor) 1:1 randomised controlled superiority trial			
Endpoints:	 1.6.1 Primary endpoints 1) PTSD symptom severity assessed by the PCL-5. 1.6.2 Secondary endpoints 1) PTSD diagnosis assessed by the CAPS-5. 			
	 2) The impact of the person's mental health on work, home, social and private leisure activities and 			

	interpersonal relationships assessed by the Work and Social Adjustment Scale.		
	3) Depression assessed by The Patient Health Questionnaire (PHQ9).		
	4) Health status assessed by The EQ5D-5L.		
	5) Self-rated self-esteem assessed by The Self-esteem scale.		
Sample Size:	215		
	•UK based military veterans from the Royal Navy or Royal Marines, British Army, Royal Air Force		
	•Male and female military veterans ≥18 years		
	•Ability to read and speak English		
Summary Of Eligibility Criteria:	•Experiencing clinically important symptoms of PTSD of >32 on the PCL5		
	•Self-reported history of exposure to one or more traumas		
	•Willingness to be randomised to treatment group		
	•Willingness for the therapy sessions to be video recorded		

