8.9 Therapist recruitment and eligibility assessment

The trial requires twelve therapists to competently deliver FIRST as per the intervention delivery timeline. We recognise that twelve therapists introduces variability, of therapist effect for example [86] [87] but this is offset with the advantages of twelve providing greater external validity. Existing Inspire therapists who achieved competence while delivering therapy in the feasibility trial will be invited to apply to join the trial. Additionally, we will recruit 8-10 independently employed therapists who meet the following criteria:

- Hold full clinical registration with either the British Association for Counselling and Psychotherapy (BACP), the National Counselling and Psychotherapy Society, Accredited Professional Registrant (NCPS Acc.) the British Association of Behavioural and Cognitive Psychotherapy (BABCP), the United Kingdom Council of Psychotherapy (UKCP), the Irish Council for Psychotherapy (ICP), or equivalent.
- Candidates will be considered if they have completed their core training hours under a UKCP, ICP or BABCP approved training organisation and have completed a minimum of 250 client contact hours under clinical supervision.
- Practitioner Clinical/Counselling Psychologists must be registered with the Health Care Professions Council (HCPC).
- Trained in RTM, NLPt Trauma Therapy or Rewind technique.
- Current Professional Indemnity Insurance to £2.5 million.
- Clinical supervision with a BACP/UKCP/ICP/BABCP/HCPC accredited supervisor.
- Access NI, Garda vetting or mainland UK DBS equivalent clearance.
- Attended certified Safeguarding, Child Protection and Adults at Risk or in Need of Protection minimum level 2 training within the last three years.
- Work to the third sector delivery partners Risk Assessment, Management and Escalation Guidelines with adherence to regional Child Protection and Vulnerable Adults in need of protection policies, procedures and good practice guidance.
- Comply fully with the standards and key performance indicators set out in Inspire's associate counsellor agreement.
- Able to commit to the time required to complete the trial.

Once eligibility is determined they will be onboarded into Inspire as Associate Therapists. Inspire onboarding will comprise:

- Access NI or DBS clearance
- Induction into Inspire's operation and clinical policies and procedures
- Induction to Inspire's information management system

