ii) The primary outcome analysis will estimate the difference in PCL-5 at 20 weeks between the two treatment groups (FIRST vs. WL) by using a linear mixed model to account for the repeated measures of PCL-5 in time. The model will include the measurements of baseline PCL-5, treatment indicator, centre indicator and group indicator as covariates. The linear mixed model of PCL-5 (outcome) will include the repeated measures of PCL-5 at baseline, time 2 (6 weeks), time 3 (12 weeks) and time 4 (20 weeks), with time as fixed effect and patients as random effect, the treatment indicator, and will be adjusted by the stratification factors, and any other prespecified factor. We will also include a time by treatment interaction term. As a secondary analysis of the primary endpoint, we will estimate the difference between the groups in the proportion of patients that reach the MCID using a chi-square test. A statistical analysis plan (SAP) outlining analyses of primary and all secondary outcomes will be written and signed off before any look at the data.

Criteria for measuring compliance to the interventions will be pre-specified. In order to account for therapist effect in the analysis of the primary outcome, PCL-5, we will use a linear mixed model, to account for the repeated measures of PCL-5 in time and that will include "therapist" as a factor. Because of the number of therapists (12 therapists), "therapist" will be included in the model as a fixed effect. Hence the linear mixed model of PCL-5 (outcome) will include the repeated measures of PCL-5 (at baseline, time 2 (6 weeks), time 3 (12 weeks) and time 4 (20 weeks)), with time as
fixed effect, patients as random effect, the treatment indicator, therapist as fixed effect, the other stratification factors, and any other prespecified factor. We will also include a time by treatment interaction term. Similarly, therapist effect will also be accounted for in the analysis of WSAS, PHQ-9, EQ5D-5L and the Self-esteem scale.

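### The 90% power in section 10.6 makes no allowance for therapist clustering in the FIRST arm, although the protocol recognises therapist effect and plans to account for it

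*Protocol*

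**What the plan says.** Section 10.6 sizes the trial "To detect a mean between group difference of 10-point drop in PCL-5 score (MCID") at 20 weeks, "with a standard deviation of 20, taken from our feasibility trial", and concludes that "90% power (5% significant level), 172 in total (86 patients per group) are required". It then allows 20% loss to follow-up and recruits 215. Neither an ICC nor a design effect appears there, and no therapist ICC is given anywhere else in the protocol.

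Section 8.9 calls for twelve therapists and says: "We recognise that twelve therapists introduces variability, of therapist effect for example". It regards this as offset by better external validity. Under sections 8.6 and 8.10.2 the waiting list receives FIRST only after the 20-week data are collected, so it has no trial therapist before the primary endpoint.

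Section 11 describes the primary analysis twice. The first description is a mixed model "with time as fixed effect and patients as random effect, the treatment indicator, and will be adjusted by the stratification factors"; it has no therapist term. The second begins "In order to account for therapist effect in the analysis of the primary outcome, PCL-5, we will use a linear mixed model" and adds therapist as a fixed effect beside the treatment indicator, giving the number of therapists as the reason. Both adjust for or include baseline PCL-5.

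**The concern.** Patients are randomised individually, but those in the FIRST arm share therapists and those on the waiting list do not. If therapists differ in their results, outcomes within a therapist's caseload are correlated. The FIRST-arm mean is then less precise than 86 independent patients would make it, and the between-therapist part of its variance rests on only 12 units.

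The protocol recognises this when it describes the therapists and again when it describes the analysis, but not when it sizes the trial. Two things are at stake. The 90% may belong to a different design from the one being run. And if the model without a therapist term is used for the primary test, its standard error would be too small when therapists are regarded as a sample from those who might deliver FIRST.

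**Working it through.** **Inputs from the protocol.** Difference 10, SD 20, 86 per group, 5% significance and 20% loss (section 10.6); 1:1 allocation (section 1.6); 12 therapists (section 8.9). The significance level is taken as two-sided, which reproduces the stated figure. The ICC is an assumption and is shown over a range.

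**Step 1: the plan's own figure.** With independent patients, SE = 20 × √(1/86 + 1/86) = 3.050 and 10/3.050 = 3.279. The non-central t on 170 df gives power 90.3%. At 85 per group it gives 89.99%, so 86 is the smallest number that reaches 90%. Then 172/0.8 = 215. Both figures reproduce exactly, and they do so with no design effect.

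**Step 2: clustering in the FIRST arm only.** Mean caseload m = 86/12 = 7.17. The FIRST-arm design effect is DE = 1 + (m − 1) × ICC. The variance of the difference is V1 + V2, with V1 = 400 × DE/86 and V2 = 400/86 = 4.651. Satterthwaite df = (V1 + V2)² / (V1²/11 + V2²/85). Power comes from the non-central t.

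| Assumed ICC | DE | V1 | SE | df | Power |
|---|---|---|---|---|---|
| 0.01 | 1.062 | 4.938 | 3.097 | 37.2 | 88.2% |
| 0.02 | 1.123 | 5.225 | 3.143 | 35.6 | 87.2% |
| 0.05 | 1.308 | 6.085 | 3.277 | 31.8 | 84.1% |
| 0.10 | 1.617 | 7.519 | 3.489 | 27.5 | 79.0% |

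About one point of the loss comes from the fewer degrees of freedom: the same formula at ICC 0 gives 89.2%. A normal approximation, which ignores the degrees of freedom, gives 89.8%, 88.9%, 86.3% and 81.8% for the four rows. A simulation of 8,000 trials with a test that respects the clusters gave 84.7% at ICC 0.05 and 78.6% at 0.10.

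**Step 3: what could restore the power.** These use ICC 0.05. Baseline adjustment is taken to reduce all variance by the factor 1 − R², leaving the ICC unchanged.

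- R² = 0.16 (correlation 0.4): SE = 3.277 × √0.84 = 3.003, power 89.8%.
- R² = 0.25 (correlation 0.5): SE = 3.277 × √0.75 = 2.838, power 92.7%.
- SD 18, the 20-week value for the RTM arm in section 9.2, unadjusted: SE = 3.277 × 18/20 = 2.949, power 90.8%. At ICC 0.10 the same SD gives 86.7%.

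**Step 4: type I error if therapist is left out.** With therapists regarded as random, the true SE exceeds the naive one by √((DE + 1)/2). This is 1.074 at ICC 0.05 and 1.144 at ICC 0.10. The two-sided error 2 × [1 − Φ(1.96/ratio)] is 6.8% and 8.7%. Simulation gave 6.9% and 8.3%.

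**Step 5: therapist as a fixed effect.** Before 20 weeks every FIRST patient has a therapist and no waiting-list patient does, so the 12 therapist indicators add up to the treatment indicator. The two cannot be estimated together without a constraint or an averaging rule, and section 11 states neither. If software resolves this by making one therapist the reference, the treatment coefficient compares about 7 patients with 86. At a single time point, unadjusted, SE = √(400/7.17 + 400/86) = 7.78, and power for 10 points is about 25%.

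**The case against.** The strongest defence is that no shortfall has been shown. The ICC is assumed. The analysis adjusts for baseline PCL-5 while section 10.6 takes no credit for it. The PCL-5 SDs reported elsewhere in the protocol (17 and 18 in section 9.2; 12.66 to 16.00 in section 5.5) are all below 20. This stands. A reader might infer that the trial's power is 84%, or that the trial is underpowered. The documents support neither: 84% needs an ICC of 0.05 that they do not give, and step 3 shows that ordinary baseline adjustment or SD 18 could bring power back to about 90% at that ICC. Nor is there an arithmetic error in 172 or 215.

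A second defence is that a fixed therapist effect conditions on these 12 therapists and so carries no random-therapist design effect. That is right in principle, but only once the collinearity in step 5 is resolved. Even then the result would speak for these 12 people, whereas section 8.9 appeals to external validity and section 4.6 looks to wider therapist training across the NHS.

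A third is that therapist variability was considered, and that detail can wait for the analysis plan. Section 8.9 does consider it, but external validity does not offset lost precision. The sample-size statement, the number of therapists and the fixed-effect coding are all set in the protocol itself.

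**Conclusion.** The concern holds as a gap in the justification. The 90% in section 10.6 is the power for 172 independent patients and omits a source of variance that the protocol recognises elsewhere. On the protocol's difference and SD, unadjusted power runs from about 88% to 79% for assumed ICCs of 0.01 to 0.10. This takes therapists as random, caseloads as equal and the total SD as 20 in both arms. Whether the planned, baseline-adjusted analysis falls short of 90% cannot be settled without an ICC and a baseline correlation, neither of which is given.

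The analysis text adds to the difficulty. The model without a therapist term would run a two-sided error of about 7% at ICC 0.05 and 9% at ICC 0.10 under random therapists. The fixed-effect version is collinear with treatment as written. This should be corrected, but it does not call for more patients.

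**What to change.** Keep N = 215. In section 10.6, restate the power for a design clustered in one arm: 12 therapists, about 7 analysed patients each, an assumed therapist ICC with its source, and power over a range. For instance, before baseline adjustment, 86 per group gives about 84% at ICC 0.05, 87% at 0.02 and 79% at 0.10. If credit for baseline adjustment or a smaller SD is wanted, state the correlation or SD assumed and the resulting power.

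In section 11, name one primary model, with a therapist random effect that applies to FIRST-arm patients only and small-sample degrees of freedom. Sizing and test then rest on the same structure, and the collinearity disappears. The cost is a few sentences in the protocol and matching wording in the analysis plan. The downside is a stated power that may be slightly less favourable.

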10.7 Internal pilot

The internal pilot will monitor recruitment, randomisation, retention in research to 12 weeks and safety of those in the WL group whose symptoms may escalate while awaiting therapy. Recruitment targets and progression criteria for the internal pilot are in table 4. Progression targets are based on an 70% retention to 12 weeks.

Table 6: Internal pilot recruitment targets and progression criteria using traffic light system (green represents 100% concordance with planned targets)

Criteria and targets	Month 1	Month 2	Month 3	Month 4	Month 5	Total
Expressions of interest (EOI) through social media campaign no, (%	91 (100%)	118 (100%)	136 (100%)	136 (100%)	136 (100%)	618 (100%)
of green target)	64	83	95	95	95	433

	(70%)	(70%)	(70%)	(70%)	(70%)	(70%)
	<64	<83	<95	<95	<95	<433
Assessed for eligibility min 24% of EOI	23	30	34	34	34	155
	16	21	24	24	24	109
	<16	<21	<24	<24	<24	<109
Recruited (consented) (min 10% of EOI)	10	12	14	14	14	64
	7	8	10	10	10	45
	<7	<8	<10	<10	<10	<45
33% of veterans recruited, who are any	2	4	4	5	5	20
of: female sex,	1	1	2	2	3	9
over 70yrs, ethnic minority	<1	<1	<2	<2	<3	<9
Randomisation targets (number of people)	10	11	13	13	13	60
(number of people)	4	8	10	10	10	42
	<4	<8	<10	<10	<10	<42
Completeness of primary outcome data: 70-100% of the total recruited population				≥80% of 34= 27	≥80% of 47 = 38	≥80% of 60 = 48
providing 12-week data				70 - 79% of 22 = 15-17	70 - 79% of 32 = 22-25	70 - 79% of 42 = 29-33
				<15 (<70%)	<22 (<70%)	<42 (<70%)

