4.4 Methods

The trial is a patient-level 1:1 computer randomised controlled trial preceded by a single arm proof of concept study. The trial incorporates a five-month internal pilot, a nested mechanistic experimental study and 52-week maintenance of effect analysis. Over 20 months we will recruit 215 UK military veterans with PTSD and randomise them to immediate FIRST therapy or five-month waiting list control. FIRST is delivered online via trained, supervised, charity partner therapists. Primary trial outcome is PTSD symptoms assessed by the PCL-5. Cognitive outcomes align with mechanistic hypotheses. The final trial follow-up on all outcomes is 20-weeks.

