4.5 Timelines for delivery

This is a forty-eight-month (M) trial: M 1-6 are set up, training and KCL ethical approval. M7-12 is proof of concept. The trial commences M 14 with internal pilot and reporting (M 14-18 and recruitment, randomisation and baseline data collection continuing to M 32. Therapy delivery and final 20-week follow up data collection M 15 to 38. Data analysis and maintenance of effect data collection M 39-46. Reporting and dissemination concludes M 47-48.

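### Table 6's 12-week completeness row mixes denominators, so its bands overlap and leave gaps, and its green counts cannot be reached within the five-month pilot

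*Protocol*

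**What the plan says.** Section 4.4 states: "The trial incorporates a five-month internal pilot". Section 4.5 dates it: "The trial commences M 14 with internal pilot and reporting (M 14-18". Section 10.7 lists among the things to be monitored "retention in research to 12 weeks" and adds "Progression targets are based on an 70% retention to 12 weeks".

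The last row of Table 6 sets traffic-light counts for participants providing 12-week primary outcome data. The population is described as "70-100% of the total recruited population". The cells are:

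| Band | Month 4 | Month 5 | Total |
|---|---|---|---|
| Green | 80% of 34 = 27 | 80% of 47 = 38 | 80% of 60 = 48 |
| Amber | 70–79% of 22 = 15–17 | 70–79% of 32 = 22–25 | "70 - 79% of 42 = 29-33" |
| Red | below 15 | below 22 | below 42 |

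Every red cell is also labelled as under 70%.

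**The concern.** A traffic-light criterion needs every possible result to fall in exactly one band, and needs each band to be attainable when the criterion is read. This row appears to fail both tests. Green is worked out on one denominator and amber on another, and the red limit changes denominator between columns. The counts are also set against nearly everyone randomised, although a participant cannot contribute 12-week data until about 2.8 months after randomisation.

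What is at stake is whether the pilot can say anything about retention. A pilot with good retention could be labelled red or receive no label. Those reading it would then have to decide after seeing the data which denominator was meant, and pre-specified criteria exist to avoid that.

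**Working it through.** **Inputs, all from Table 6 unless stated**

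- Green randomisation targets by month: 10, 11, 13, 13, 13; cumulative 10, 21, 34, 47, 60.
- Amber randomisation targets by month: 4, 8, 10, 10, 10; cumulative 4, 12, 22, 32, 42.
- Consented targets by month: 10, 12, 14, 14, 14; cumulative 10, 22, 36, 50, 64.
- Pilot length five months, including reporting (sections 4.4 and 4.5).
- Assumption: 365.25/12/7 = 4.348 weeks per month, so 12 weeks = 12/4.348 = 2.76 months.

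**1. Reproducing the printed counts**

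- Green: 0.80 × 34 = 27.2; 0.80 × 47 = 37.6; 0.80 × 60 = 48.0. These match on the green randomisation targets.
- Amber: 0.70 to 0.79 × 22 = 15.4 to 17.4; × 32 = 22.4 to 25.3; × 42 = 29.4 to 33.2. These match on the amber randomisation targets.
- Red: 0.70 × 22 = 15.4 and 0.70 × 32 = 22.4 match months 4 and 5 on the amber denominators. In the Total column the same rule gives 0.70 × 42 = 29.4, but 42 is printed, and 42 = 0.70 × 60.

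The denominators are therefore randomised counts. The row label speaks of those recruited, for whom the cumulative figures would be 36, 50 and 64.

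**2. Where each Total count falls**

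| Participants with 12-week data | Bands that apply |
|---|---|
| up to 28 | red |
| 29–33 | amber and red |
| 34–41 | red only |
| 42–47 | none |
| 48 or more | green |

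Month 4 has no band for 18–26, and month 5 has none for 26–37. Three examples from the Total column, each with all randomised participants already due:

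- 42 randomised, 41 give data: 41/42 = 98%, reads red.
- 45 randomised, 80% give data: 0.80 × 45 = 36, reads red.
- 60 randomised, 29–33 give data: 29/60 = 48% to 33/60 = 55%, yet the count falls in the cell labelled 70–79%.

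**3. How many can have reached 12 weeks**

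Take accrual exactly at the green targets and no loss at all.

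- End of month 4, even accrual: 4 − 2.76 = 1.24 months of accrual are due, so 10 + 0.24 × 11 = 12.6.
- End of month 5, even accrual: 5 − 2.76 = 2.24 months are due, so 10 + 11 + 0.24 × 13 = 24.1.
- Ceiling, everyone randomised on the first day of each month: two monthly cohorts are due at month 4 (10 + 11 = 21) and three at month 5 (21 + 13 = 34).
- Floor, everyone randomised at month end, or even accrual with 4-week months: 10 and 21.
- If the last participant is randomised at the end of month 5, all 60 are due at 5 + 2.76 = about month 7.8.

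| Column | Possible with perfect retention | Green needs | Reading |
|---|---|---|---|
| Month 4 | 10 to 21; about 13 if even | 27 | red if even; 21 falls in the gap |
| Month 5 | 21 to 34; about 24 if even | 38 | amber if even; 21 is red, 34 falls in the gap |
| Total, read at end of month 5 | 21 to 34; about 24 if even | 48 | below 42, so red throughout (29–33 also amber) |

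The month-4 and month-5 denominators, 34 and 47, are everyone randomised by the end of months 3 and 4. That is a lag of one month where 2.76 is needed.

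**The case against.** **The Total column carries no reading date.** It may mean the whole pilot cohort once everyone has been followed up. Read that way, 60 of 60 is green, so a reader who infers that perfect retention always reads red goes too far. This stands. Against it, section 4.5 places pilot reporting within M14–18, and nothing in section 10.7 defers the retention reading. Section 11 speaks of adjustment after month 12, but that sentence concerns recruitment targets and the campaign. The month-4 and month-5 columns carry their own dates in any case, and green is out of reach in both. Waiting would cure the timing but not the bands.

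**The red limit of 42 looks like a clerical slip.** The other two red cells follow the amber denominators, which would give about 29 here, and below 42 is also the red cell in the randomisation row just above. This is plausible. Correcting it would remove the overlap but leave 34–47 with no band, and the gaps at months 4 and 5 would remain.

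**The printed percentages already form a rule.** They do, but on two different denominators, and neither is the number due at 12 weeks.

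**Stronger inferences are tempting.** A reader might conclude that the table fails the trial on retention whatever participants do. The protocol calls these progression criteria but attaches no action to any colour, and month 5 can reach amber. A reader might also set the 70% basis against section 10.6, "To allow for a loss to follow up of 20% at 20 weeks", and infer a loss of power. An amber band below the planning value is how traffic-light systems ordinarily work. Completeness at 12 weeks is not the evaluable fraction at 20 weeks, and the planned mixed model (section 11) uses the 6- and 12-week PCL-5 as well. Neither inference is supported.

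**Conclusion.** The completeness row is wrong as written, in two separable ways.

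- **Bands.** This holds whatever the reading date and needs no assumption beyond the printed cells. In the Total column five counts (29–33) carry two colours, eight (34–41) are red although above amber, and six (42–47) carry none.
- **Timing.** This rests on accrual at the printed green targets and on reading within the five-month pilot. Green is then unreachable in every column under each accrual pattern tried: at most 21 against 27, 34 against 38, and 34 against 48. The firm red result under perfect retention is the Total column read at the end of month 5. Month 4 is red under even accrual but not under every pattern.

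The defect is confined to the pilot's retention criterion. It does not touch the primary analysis, the sample size or the randomisation.

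**What to change.** Replace the fixed counts in this row with one proportion: participants with a completed 12-week PCL-5, divided by participants whose 12-week date has passed at the data cut. Use contiguous bands on that single denominator: green at 80% or more, amber at 70–79% (70% to below 80%), red below 70%. Delete the red limit of 42, bring the row label into line with the new denominator, and state the date on which the row is read.

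The pilot decision need not move. Read at the end of month 5, the proportion rests on about 24 participants, so it is less precise than one based on 60. At a true 80% the standard error is √(0.8 × 0.2/24) = 8 percentage points, against √(0.8 × 0.2/60) = 5. Completion of the 6-week PCL-5 can be shown beside it as supporting information: 6/4.348 = 1.38 months, so 3.62 months of accrual are due, 34 + 0.62 × 13 = about 42 participants.

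The cost is one rewritten table row and a sentence giving the reading date. No new data are needed.
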